2.2. Schedule of Events

Table 2-1: Schedule of Events

Day(s)	Screening	Administration Period														ET	FU		
		1-2 ^a				4 ^b	7 ^{a,b}	10 ^b	18 ^b	28 ^b	42 ^b	56-57 ^a							
Window	-	-				±1	±1	±1	±1	±1	±1	±1				-	±1		
Time from Admin. (hr.)		Pre-dose	0	4	10	24 ^c						Pre-dose	0	4	10	24 ^c			
Informed consent	X																		
Inclusion/Exclusion	X																		
Medical history	X																		
Concomitant medications	X	X					X	X	X	X	X	X					X	X	X
Physical exam ^d	X	X	X	X	X	X	X	X	X	X	X	X	X	X	X	X	X	X	X
Vaginal speculum exam ^e	X	X				X		X		X	X	X					X	X	X
Mammogram ^f	X																		
Cervical screening test ^g	X																		
Height and weight	X																		
Vital signs ^h	X	X		X	X	X		X		X	X	X		X	X	X	X	X	X
12-Lead ECG ⁱ	X	X		X				X		X	X		X		X		X	X	X
Serum biochemistry	X	X						X		X	X						X	X	X
Hematology	X	X						X		X	X						X	X	X
Urinalysis	X	X						X		X	X						X	X	X
Coagulation panel	X	X						X		X	X						X		X
TSH	X																		
FSH ^j	X																		
Drugs of abuse ^k	X																		
Viral serology ^l	X																		
Vaginal pH ^m	X	X							X	X	X						X	X	X
Vaginal cytology	X	X							X	X	X						X	X	X
Transvaginal ultrasound	X ⁿ																X	X	
Assessment of VVA symptoms ^o	X								X	X	X	X						X	X
Diary administration and review ^p	X	X					X	X	X	X	X	X						X	
Study drug administration ^q			X			X	X	X	X	X	X		X						
MENQOL		X															X	X	
Usability and Acceptability questionnaire						X					X						X	X	
PK blood samples ^r		X	0.5, 1, 2, 4, 5, 8, 12 (hr.)		X	X	X	X	X	X	X	X	0.5, 1, 2, 4, 5, 8, 12 (hr.)	X					X
AE ^s		X	X	X	X	X	X	X	X	X	X	X	X	X	X	X	X	X	X

Abbreviations: AE = adverse event; ECG = electrocardiogram; ET = early termination; FSH = follicle-stimulating hormone; FU = follow-up; HBsAg = hepatitis B surface antigen; HCV = hepatitis C virus; HIV = human immunodeficiency virus; hr. = hour; IP = investigational product; MENQOL = Menopause-specific Quality of Life; PK = pharmacokinetics; TSH = thyroid-stimulating hormone; VVA = vulvar vaginal atrophy

- a. Multiple non-PK assessments scheduled for the same time point should be performed on the same day as dosing. PK blood sample procedures should follow the defined window, if applicable.
- b. Samples for PK trough levels should be obtained prior to DARE-VVA1 insertion on Days 4, 7, 10, 18, 28, and 42. Administration of DARE-VVA1 will take place at site on the day of these visits, after collecting the trough PK sample.
- c. Participants will be discharged from the site after all 24-hour assessments have been completed. Day 1-2 only: Administration of DARE-VVA1 should be the final activity before discharge, following completion of all 24-hour assessments.
- d. A complete physical examination (excluding rectal examinations) will be performed at screening and will include a manual breast examination. Subsequent physical examinations will be abbreviated and will be directed based on signs and symptoms exhibited by the participant.
- e. Vaginal speculum examinations will include assessment of local irritation (scoring of erythema and edema), and a full pelvic examination.
- f. Mammograms should be conducted ONLY in those participants who have not had one within the last 2 years.
- g. Cervical screen testing should be conducted ONLY in those participants who have a cervix and have not had cervical screening within the last 5 years.
- h. Vital signs assessments will include pulse rate, respiratory rate, and supine blood pressure. Assessments will be performed after the participant has been in a supine position for at least 5 minutes. Temperature will also be measured.
- i. 12-lead ECGs will be performed after the participant has been supine for at least 5 minutes.
- j. FSH will be assessed in all hysterectomized women who have not undergone bilateral oophorectomy, and in non-hysterectomized women who have not undergone bilateral oophorectomy and have experienced spontaneous amenorrhea for ≥ 6 months but < 12 months, to confirm postmenopausal status.
- k. Drugs of abuse will be measured at screening by local laboratories via urinalysis and alcohol screens versus a commercially available urine dipstick.
- l. Viral serology: a blood sample will be collected for the determination of HIV, HCV, and HBsAg.
- m. Vaginal pH will be evaluated using commercially available pH strips.
- n. Transvaginal ultrasound will be performed on women who have not undergone a hysterectomy. During screening, the pelvic examination, with assessment of local irritation and cervical screening (if needed), should be performed prior to the transvaginal ultrasound.
- o. Participants will be required to engage in vaginal intercourse or other sexual activity (masturbation, etc.) at least 1 time between Days 49-56, and complete an assessment of VVA symptoms in their diary.
- p. Diaries will be provided to participants at screening, and participants will be trained on their completion. Participants will record their administration of DARE-VVA1 in the diary, including the time of placement. Study staff should instruct participants to bring their diaries to all site visits for review.
- q. On Days 4, 7, 10, 18, 28, and 42, participants should not self-administer the IP at home; blood samples for trough PK assessments should be collected at site before the IP is administered.
- r. Permissible windows for PK sampling are as follows: 0.5 hours and 1 hours = ± 10 minutes; 2, 4, 5, 8, 12, and 24 hours = ± 15 minutes. Trough samples collected on Days 4, 7, 10, 18, 28, and 42 should be collected within 30 minutes before IP administration.
- s. Adverse event information will be collected at the specified time points, as well as at any time when a clinical research unit staff member becomes aware of an AE during the administration period.

4. LIST OF ABBREVIATIONS AND DEFINITION OF TERMS

ABBREVIATION	EXPLANATION
λ_z	terminal rate constant
ADR	adverse drug reaction
AE	adverse event
AI	aromatase inhibitor
APTT	activated partial thromboplastin time
ATC	Anatomical Therapeutic Chemical
AUC	area under the plasma concentration-time curve
BMI	body mass index
BP	blood pressure
C_{max}	maximum observed plasma drug concentration
CRA	clinical research associate
CRF	case report form
CSR	clinical study report
CST	cervical screening test
DMP	data management plan
DVT	deep vein thrombosis
ECG	electrocardiogram
EDC	electronic data capture
eCRF	electronic case report form
FSH	follicle-stimulating hormone
FU	follow-up
GCP	Good Clinical Practice
HBsAg	hepatitis B surface antigen
HCV	hepatitis C virus
HIV	human immunodeficiency virus
hr.	hour
HR+	hormone receptor-positive
HREC	Human Research Ethics Committee
IB	Investigator's Brochure
ICF	informed consent form
ICH	International Council for Harmonisation of Technical Requirements for Pharmaceuticals for Human Use
INR	International Normalized Ratio
IP	investigational product
ITT	intent-to-treat

ABBREVIATION	EXPLANATION
NYHA	New York Heart Association
MedDRA	Medical Dictionary for Regulatory Activities
MENQOL	Menopause-specific Quality of Life (questionnaire)
OTC	over-the-counter
Pap	Papanicolaou (test)
PD	pharmacodynamics
PE	pulmonary embolism
PK	pharmacokinetics
PT	prothrombin time
RBC	red blood cell
SADR	serious adverse drug reaction
SAE	serious adverse event
SAP	statistical analysis plan
SD	standard deviation
SERM	selective estrogen receptor modulator
THC	tetrahydrocannabinol
TIA	transient ischemic attack
$t_{1/2}$	plasma terminal half-life
T_{max}	time of occurrence of maximum observed plasma drug concentration
TSH	thyroid-stimulating hormone
UTI	urinary tract infection
VVA	vulvar and vaginal atrophy
WHO-DD	World Health Organization Drug Dictionary

5. INTRODUCTION

5.1. Background and Rationale

Vulvar and vaginal atrophy (VVA) is a common and underreported condition that is a result of decreased estrogenization leading to thinning of the vaginal epithelium.^{1,2} Typical symptoms include vaginal dryness, itching, burning, and painful intercourse, adversely impacting quality of life. Clinical findings include the diagnostic presence of pale and dry vulvovaginal mucosa with petechiae, as well as a vaginal pH > 5. Vulvar and vaginal atrophy most commonly occurs in the postmenopausal phase, during which the prevalence is close to 50%.³

Over-the-counter (OTC) remedies such as vaginal moisturizers and lubricants can provide temporary symptomatic treatment at the time of use. Localized estrogen therapy (i.e., estrogen-containing creams, rings, and suppositories) can treat the underlying physiologic issue and is the most commonly prescribed treatment by physicians for VVA. However, this therapeutic approach is contraindicated for women with hormone receptor-positive (HR+) breast cancer. In addition to surgery and/or radiation, many of these women are treated with aromatase inhibitors (AIs), which deplete the body of estrogen and induce a menopausal state irrespective of age. Consequently, the prevalence of VVA in HR+ breast cancer survivors is an estimated 70%.^{4,5} Although localized estrogen therapy is highly effective in reducing the symptoms of VVA in otherwise healthy women, it is a suboptimal intervention for HR+ patients and survivors because of the prolific response of these tumors to the presence of estrogen in the surrounding tissue. As a result of this safety concern, the current estrogen products on the market for the treatment of VVA are labeled as being contraindicated when the patient has a “known, suspected, or a history of breast cancer”. Oncologists, obstetricians, gynecologists, and primary care providers are reluctant to prescribe any estrogen-based products owing to concerns of reintroducing estrogen into the system, despite the low dose and topical delivery.

Daré Bioscience, Inc. (Daré) is developing a novel local application of tamoxifen to mitigate the symptoms of VVA for patients with or at risk for HR+ breast cancer, including women currently on anticancer therapy. There remains a large unmet need for a novel nonhormonal VVA treatment specifically developed for this subset of cancer patients and survivors, and other women who require or prefer a treatment option that does not contain estrogen.

Selective estrogen receptor modulators (SERMs) represent an exciting new option for the treatment of VVA in an HR+ patient population. Tamoxifen is a well-known and well-characterized SERM that has been prescribed by oncologists for decades for the treatment of breast cancer. Tamoxifen acts as an estrogen antagonist in the breast; it binds estrogen receptors in the breast tissue, effectively blocking natural estrogen from binding to these sites, and is therefore an effective HR+ breast cancer treatment. In contrast, in other tissues such as uterine and vaginal tissues, tamoxifen acts as an estrogen agonist, producing similar physiological responses to those produced by estrogen, without being a true estrogen.

Studies of tamoxifen conducted over the last 40 years have documented the estrogen-like effects of this SERM on vaginal epithelium.⁶⁻¹⁴ A preliminary clinical study of intravaginally administered tamoxifen in postmenopausal women further supports the potential for locally administered tamoxifen to have positive effects that counter VVA in the vaginal tissue without significant systemic absorption (see Section 5.3). Localized tamoxifen therapy thus has the potential to counter the physiologic changes that lead to VVA without introducing estrogen back into the system. Together, these studies establish a strong scientific rationale for the continued

development of DARE-VVA1, as a novel intervention expected to modulate the symptoms of VVA in an HR+ breast cancer population without the use of estrogen-based hormones.

5.2. Nonclinical Experience

Vaginal tamoxifen has been evaluated in rats and rabbits. In a 3-day repeat-dose study (Study 3015-001) in ovariectomized female rats, intravaginal tamoxifen was evaluated at doses of 0.2 mg/kg/day, 2.0 mg/kg/day, and 20 mg/kg/day.¹⁵ No vaginal irritation was observed at any dose. A dose-dependent increase in uterine wet weight was observed at all dose levels, which correlated with luminal epithelial and myometrial hypertrophy and stromal hypertrophy/hyperplasia. Microscopic evaluation showed minimal to mild focal erosions in the vagina at the highest dose and mild epithelial hyperplasia at all doses. A 28-day study in rabbits (Study 2110-001) evaluated 2 doses (1 mg and 20 mg) of tamoxifen. Inappetence was observed, and body weight gain was reduced at 1.0 mg, while body weight loss was observed at 20 mg. No test article-related vaginal irritation was observed, with sporadic findings of erythema and edema comparable to those seen in vehicle-treated animals.

From previous studies in rabbits, the absorption of tamoxifen from the vagina is expected to be relatively rapid. In rabbits, the T_{max} was 0.5 to 1.0 hour following vaginal administration of 1.0 mg and 20 mg tamoxifen. As stated above, this formulation is designed to release tamoxifen rapidly following disintegration of the gelatin capsule. The time points in the DARE-VVA1-001 study were chosen to collect information over the time frame when plasma concentrations are expected to rise and reach a steady state. There are samples taken intensively over the first 24 hours and then periodically up to 8 weeks (56 days). Following oral administration of tamoxifen, T_{max} is about 5 hours. The present study will also examine PK during the time after the last dose intensely over 24 hours. As noted, tamoxifen has a long half-life following oral administration (5 to 7 days based on Nolvadex labeling¹⁶, and its metabolites can have longer half-lives). Attempting to collect data through several half-lives following the last vaginal dose would unduly prolong the study and likely not provide any new information about tamoxifen. Nonetheless, the present amendment removes 3 sampling time points on Day 1 and Day 56 (i.e., samples at 3 hours, 6 hours, and 18 hours) since these are not expected to contribute to understanding of the pharmacokinetic profiles and parameters.

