5.4. Summary of Potential Risks and Benefits

The potential benefits of study participation are that participants with VVA may experience a reduction in the symptoms associated with VVA as a result of treatment with DARE-VVA1. No other benefits of participation are anticipated.

The potential risks of study participation include those associated with exposure to tamoxifen and the excipients found in DARE-VVA1 and the risks of medical evaluation, including venipuncture.

Oral tamoxifen (tablets or solution) is approved for the treatment of estrogen receptor-positive metastatic breast cancer and to reduce the risk of breast cancer in women at high risk.¹⁸ The label includes a boxed warning concerning the risk of uterine malignancies, stroke, and pulmonary embolism. General warnings include risks of thromboembolic events (although this risk is greater when co-administered with chemotherapy), embryo-fetal toxicity (which is not a risk in the present study population), and liver cancer and liver abnormalities.

The National Surgical Adjuvant Breast and Bowel Project reported relative risks of serious events in a double-blind, placebo-controlled study of 5 years' treatment with tamoxifen (20 mg per day) designed to evaluate whether treatment would reduce the incidence of invasive breast cancer in high-risk women. After a median treatment duration of 3.5 years in 13,388 women, the rates (per 1,000 women per year) for major outcomes were as follows:

Major Outcomes	Rates for tamoxifen (per 1,000 women per year)	Rates for placebo (per 1,000 women per year)
Endometrial adenocarcinoma	2.20	0.71
Uterine sarcoma	0.17	0.0
Stroke	1.43	1.00
Pulmonary emboli	0.75	0.25
Deep vein thrombosis	1.26	0.79
Cataracts	25.41	22.51

Source: Soltamox label¹⁸

In addition to these serious risks, the most common adverse reactions with oral tamoxifen include hot flashes, mood disturbances, vaginal discharge, vaginal bleeding, nausea, and fluid retention.¹⁸

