10.3.1.2 Clinical Examinations

10.3.1.2.1 Vital Signs

Vital signs, including pulse rate, respiratory rate, and blood pressure in accordance with the schedule of events (Table 2-1). Assessments will be performed after the participant has been in a supine position for at least 5 minutes. Temperature will also be measured.

Normal ranges for these parameters are as follows:

- Pulse rate: 60 to 100 beats per minute

- Systolic blood pressure: 90 to 140 mmHg
- Diastolic blood pressure: 60 to 90 mmHg
- Respiratory rate: 8 to 22 breaths per minute
- Temperature: 35.5 to 37.5°C

Weight and height will be assessed only assessed at screening.

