13.1.2.3 Demographics and Other Baseline Characteristics

These analyses will be conducted for the Safety and ITT populations.

Demographic variables will include age, height, weight and BMI. Information on race and ethnicity will be collected for any eventual analysis of differences in response to the IP, in accordance with local regulatory requirements. These will be summarized descriptively.

Baseline participant characteristics will include medical history, vaginal speculum examinations, mammograms and CSTs. These will be summarized by treatment group and overall.

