13.1.4.3 Vital Signs

Descriptive summaries (mean, SD, median, minimum, and maximum) of actual values and changes from baseline will be calculated for systolic blood pressure, diastolic blood pressure, heart rate, and respiratory rate, by treatment group.

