20. WEIGHT GAIN	 No	 Yes	 0	 1	 2	 3	 4	 5	 6	
21. INCREASED FACIAL HAIR	 No	 Yes	 0	 1	 2	 3	 4	 5	 6	
22. CHANGES IN APPEARANCE, TEXTURE OR TONE OF MY SKIN	 No	 Yes	 0	 1	 2	 3	 4	 5	 6	
23. FEELING BLOATED	 No	 Yes	 0	 1	 2	 3	 4	 5	 6	
24. LOW BACKACHE	 No	 Yes	 0	 1	 2	 3	 4	 5	 6	
25. FREQUENT URINATION	 No	 Yes	 0	 1	 2	 3	 4	 5	 6	
26. INVOLUNTARY URINATION WHEN LAUGHING OR COUGHING	 No	 Yes	 0	 1	 2	 3	 4	 5	 6	
27. DECREASE IN MY SEXUAL DESIRE	 No	 Yes	 0	 1	 2	 3	 4	 5	 6	
28. VAGINAL DRYNESS	 No	 Yes	 0	 1	 2	 3	 4	 5	 6	

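### Body weight is measured only at screening, so the weight effect seen at both doses of the 28-day vaginal rabbit study cannot be quantified or compared by arm

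*Combined protocol and SAP*

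**What the plan says.** **The animal finding.** Section 5.2 states: "A 28-day study in rabbits (Study 2110-001) evaluated 2 doses (1 mg and 20 mg) of tamoxifen". On weight it reports: "Inappetence was observed, and body weight gain was reduced at 1.0 mg, while body weight loss was observed at 20 mg". It gives no size for the effect, no rabbit body weight and no dosing frequency, and does not say whether vehicle-treated animals showed it too.

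**Measurement in the trial.** Section 10.3.1.2.1 says: "Weight and height will be assessed only assessed at screening". In Table 2-1 the row "Height and weight" carries one mark, in the screening column.

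**Use in the analysis.** Section 13.1.2.3 treats weight as a baseline descriptor: "Demographic variables will include age, height, weight and BMI". The change-from-baseline summaries in section 13.1.4.3 cover "systolic blood pressure, diastolic blood pressure, heart rate, and respiratory rate, by treatment group". Weight is not in that list.

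**A separate reason to weigh.** Section 5.4 says that "the most common adverse reactions with oral tamoxifen include hot flashes, mood disturbances, vaginal discharge, vaginal bleeding, nausea, and fluid retention".

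**Indirect capture.** Adverse events are sought at every visit with open questions (11.2.1). Examinations after screening are shortened and follow the participant's signs and symptoms (10.3.1.2.3). The MENQOL, completed before the first dose and on Day 57, includes "20. WEIGHT GAIN" and an item on feeling bloated (Appendix A).

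**The concern.** This is the first use of the product in humans, and safety and tolerability is a primary objective (section 6.1). The sponsor's repeat-dose animal study by the intended route showed a systemic effect that was worse at the higher dose. Section 7.3 relies on 28-day rabbit data at 20 mg to support the top dose, but cites only the absence of important effects on the reproductive tract. The monitoring measures in section 5.4 (ECG, liver tests, clotting, vaginal inspection, ultrasound) do not address weight or appetite, and no reason is given for leaving them out.

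At stake is whether the safety report can say by how much weight changed, and whether the change rose with dose. As planned, it can give only counts of reported events and a diluted questionnaire score. Weight loss and poor appetite, which is what the rabbits showed, have no prompted question at all.

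**Working it through.** **1. Post-baseline weights.** Table 2-1 schedules one weight, at screening, and none after dosing. Change from baseline needs at least one later value, so it cannot be computed for any of the 5 × 8 = 40 participants.

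**2. What MENQOL item 20 can show.** Appendix A converts each response to a score of 1 to 8, places items 11 to 26 (16 items) in the physical domain, and defines the total as the mean of four domain means. Section 13.1.6.3 summarises domain and total scores only. For the largest possible change in item 20, with all other items fixed:
- change in the physical domain mean = (8 − 1)/16 = 7/16 = 0.44
- change in the total = 0.44/4 = 0.11

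The item asks about gain, the opposite direction to the rabbit finding.

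**3. What adverse-event reporting can show.** The chance of at least one case among 8 women on a dose is 1 − (1 − p)^8. For assumed true rates p of 5%, 10% and 20% this is 34%, 57% and 83%. For 32 active women, 1 − (1 − p)^32 gives 81%, 97% and over 99%. This presumes that every case is noticed and reported. It detects occurrence, not kilograms.

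**4. Precision if weight were added.** The documents give no SD for weight change, so 1 to 2.5 kg over 8 weeks is assumed. The 95% half-width for a difference is t × SD × √(1/n₁ + 1/n₂).

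| Comparison | t | √ term | Half-width | SD 1 kg | SD 2.5 kg |
|---|---|---|---|---|---|
| All active v placebo (32 v 8) | 2.02 (38 df) | 0.395 | 0.80 × SD | ±0.8 kg | ±2.0 kg |
| One dose v placebo (8 v 8) | 2.14 (14 df) | 0.500 | 1.07 × SD | ±1.1 kg | ±2.7 kg |

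These figures ignore dropout. Pooling the active arms would also dilute a dose-related effect, since 24 of the 32 active women receive 1 to 10 mg.

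**5. Why a Day 1 weight is needed.** Screening may precede enrollment by up to 21 days (10.2.1). Section 13.1 takes the last pre-dose observation as baseline, so without a Day 1 weight the baseline could be three weeks old.

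**The case against.** The strongest reply is that the trial has other ways to notice such an effect, and that its relevance to women is uncertain. Much of this stands.

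- A reader might infer that the trial is blind to weight effects, or that a clean safety result would carry no information about them. The documents do not support that. Poor appetite, noticed weight change or oedema could be reported as adverse events or found on directed examination, and the MENQOL asks about weight gain and bloating. What is missing is quantification.
- A reader might take the rabbit finding and fluid retention as one signal. They act in opposite directions: the rabbits ate less and gained less or lost weight, whereas fluid retention would tend to raise weight. Fluid retention is also listed for oral dosing. Section 5.4 cites 1.0 to 10.0 ng/mL after 13 mg vaginally against an average of 122 ng/mL orally, at most 10/122 = 8%. It is a secondary reason for the same measurement.
- A reader might compare mg/kg doses and conclude that there is no margin between the low rabbit dose and the top human dose. That needs rabbit and human body weights and a rabbit dosing frequency that the documents do not give. It also ignores the twice-weekly phase: 14 + 12 = 26 inserts in 56 days, or about 26 × 20/56 = 9.3 mg/day on average at the top dose.
- A reader might expect the added data to show or exclude a 2 kg shift. At an SD of 2.5 kg the pooled half-width is itself 2.0 kg, so they could not do so reliably.
- Section 13.1.4 keeps safety analyses descriptive, so a confidence interval against placebo would be out of keeping with the plan.

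The low human exposure does not dispose of the point. It compares vaginal with oral dosing in 4 women, whereas the rabbit effect arose by the vaginal route, and no rabbit plasma concentrations are given from which to derive a margin. The Investigator's Brochure may say more but is not available here.

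**Conclusion.** The point holds as a gap in measurement. A finding at both doses of the sponsor's own 28-day vaginal study, worse at the higher dose, has no objective post-baseline measure, and the protocol does not explain the omission. Weight change cannot be quantified or compared by arm. It rests on adverse-event reports, symptom-directed examinations and a gain-only item that can move its domain mean by at most 0.44 and the total by 0.11.

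This is an inexpensive improvement to a primary safety objective, not a flaw that undermines the trial. The gap itself follows from the protocol without any assumption. The relevance of the rabbit finding to women remains open on these documents, and the precision figures depend on the assumed SD of 1 to 2.5 kg and on full follow-up.

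**What to change.** In Table 2-1 and section 10.3.1.2.1, add body weight at Day 1 (pre-dose), Day 28, Day 57 and Early Termination. In section 13.1.4.3, add weight to the variables summarised as actual value and change from baseline by treatment group, descriptively, as for the other safety variables. If the sponsor prefers not to weigh participants after screening, the protocol should say why the rabbit finding does not call for it.

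The cost is a brief weighing at visits that already take place and one more row in a descriptive table, with no new visit, staff or sample. The drawback is one more safety variable with limited precision at 8 per arm, so it should be read as descriptive only.
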